## 1 Administrative information

## 1.1 Study full title

Primary care led post-diagnostic dementia care: Feasibility and implementation study of evidence-based, person-centred sustainable models for future care.

#### 1.2 Purpose

This Statistical Analysis Plan (SAP) describes a protocol-specified analysis of the PriDem Study (Workstream 4). The SAP contains details of quantitative analyses only and does not describe any qualitative and/or economic analyses.

#### 1.3 Protocol version

This SAP has been written based on information contained in the study protocol version 6.0, dated 8 August 2022. Full details of the study design, population, intervention, comparison and outcome variables may be found in the protocol.

## 1.4 Study registration

This study was prospectively registered with ISRTCN (11677384) and IRAS (294881). Confidentiality Advisory group support has been obtained (ref.: 21/CAG/0182)

#### 1.6 SAP revisions

#### **Version History Log**

Version	Date	Changes
1.0	16/01/2023	N/A (Version 1.0)

### 2 List of Abbreviations

AE Adverse Event
AR Adverse Reaction

CAG Confidentiality Advisory Group

CI Chief Investigator

C-DEMQOL Carer specific dementia quality of life measure

CRF Case Report Form

CSRI Client Service Receipt Inventory-shortened, adapted for PriDem

DEMQOL Dementia quality of life measure
DEMQOL-proxy Dementia quality of life measure proxy

EQ-5D-5L Quality of life measure

HADS Hospital Anxiety and Depression Scale

ISRCTN International Standard Randomised Controlled Studies Number

MoCA Montreal Cognitive Assessment
NPI Neuropsychiatric inventory
PCN Primary Care Network
PLWD Person Living with Dementia

QALY Incremental cost per quality adjusted life year

QOF Quality Outcomes Framework

SAE Serious Adverse Event
SAP Statistical Analysis Plan
SAR Serious Adverse Reaction

#### 3 Introduction

#### 3.1 Background

The overall aim of the PriDem programme is to develop and evaluate an acceptable, feasible and sustainable model of evidence based, person-centred, primary care led post diagnostic dementia care to maintain and improve quality of life for people with dementia and their families. The PriDem intervention comprises multiple components which are focused on three interlinked areas of systems of support, tailored care and capacity building.

## 3.2 Principal research objectives

The primary feasibility objectives are to assess:

- The rates of recruitment and retention at follow-up.
- The acceptability and engagement with both the intervention and implementation study procedures
- The proportion of people with dementia whose notes are reviewed for service use data at participating practices.
- The number of patient records reviewed in the care plan audit (overall and by recruited practice).

The primary implementation objectives are to assess:

- If the PriDem intervention increases the number of people with dementia with a personalised care plan.
- If the PriDem intervention can be implemented in wider primary care settings.

# 3.3 Secondary research objectives

Secondary feasibility objectives are to assess:

- The feasibility and acceptability of engaging and training clinical dementia specialists and embedding within existing care pathways and models of service delivery.
- Whether the intervention can be delivered as intended.
- What are the resource requirements to access, collect and analyse the data.

• The acceptability and appropriateness of the potential primary and secondary implementation outcomes.

#### Secondary implementation objectives are:

- To examine how the intervention is delivered and adapted within practice.
- To identify context and delivery variations/factors which influence embedding the intervention components in usual care.
- To identify factors that increase adoption, coverage and sustainability of the intervention including acceptability, appropriateness, fidelity.
- To collect data on the resources needed for implementation.
- Determine the cost-effectiveness of the PriDem Intervention and its implementation.
- Explore the context, mechanisms and impact of the intervention for PLWD, CPs and professionals and the barriers and levers to implementation at scale using mixed methods, such as efficiency, safety, effectiveness, equity, patient-centredness, satisfaction and timeliness.

# 4 Study Methods

# 4.1 Study design

The study is non-randomised, will run for 15 months in total and will be conducted in four Primary Care Networks (PCNs), two in the Northeast of England and two in the South East of England.

Participating sites and participants will have exposure to the intervention over a twelve-month period. Routine and study-specific data will be collected pre-intervention (baseline), at four months and 9 months (see Protocol Version 6.0 for further details).

# 4.2 Sample size

The nature of the study (a feasibility and implementation study) implies that a power-based formal sample size calculation related to a hypothesis test of interest would not be appropriate. With regard to numbers of practices and participants: four PCNs will be recruited to participate in the study. It is anticipated that each recruited PCN will contain up to 5 practices. Within each PCN site, we aim to recruit approximately

20 people living with dementia. We expect to recruit approximately 80 participants into the study within the first four months.

It is anticipated that pre-intervention, approximately 40% of people diagnosed with dementia have a personalised care plan. Following the intervention phase, we would like this to increase to at least 50% of people diagnosed with dementia. As such, a sample size of 215 people with dementia is sufficient to detect an increase in the proportion of people with a personalised care plan of at least 0.1, using a one-sided Z-test at the 5% significance level with 90% power. This assumes that the current proportion of people who have a personalised care plan is 0.4.

## 4.3 Interim analysis

This study is low risk and therefore an interim analysis will not be undertaken. We will report on feasibility in terms of recruitment rates and completeness of data collection (as well as the acceptability and adaptation for the intervention).

# **5 Statistical Principles**

#### 5.1 Confidence intervals and p-values

The 5% level will be used to determine statistical significance and confidence intervals will be reported at the 95% level.

# 5.2 Analysis Populations

All analyses shall be performed on an intention-to-treat basis. Any participants that have withdrawn from the study, and who withdraw permission to keep and use their data, will be excluded.

# 6 Study Population

#### 6.1 Recruitment and retention

A CONSORT diagram will be presented to provide a detailed description of participant numbers at each time point during the study. In addition, a table summarising the number of participants who have been withdrawn at each stage of the study and reasons for withdrawal (if supplied) will be presented.

#### 6.2 Baseline characteristics

Demographic information collected at baseline will be presented in a table. Numerical variables will be summarised using either means and standard deviations or medians and interquartile ranges. Categorical variables will be summarised using counts and proportions. The number of missing observations will be reported.

For participants recruited to the PriDem study, the following baseline characteristics of people living with dementia and/or their carer will be summarised:

- a) Age (in years)
- b) Gender
- c) Ethnicity (defined as: [White], [Black, African, Caribbean or Black British], [Asian or Asian British], [Mixed or Multiple Ethnic Groups], [Not specified/Do not wish to specify])
- d) Site (North East or South East)
- e) Relationship of PLWD to carer (defined categories: Spouse, Partner, Son/Daughter, Son/Daughter in law, Brother/Sister, Other relative, Friend, Neighbour, Other)
- f) Dementia diagnosis (defined categories: Alzheimer's disease, Vascular, Lewy Body, Mixed, Other or Unknown)
- g) Time since dementia diagnosis
- h) Social deprivation score (using the postcode-based Index of Multiple Deprivation (IMD) quintile)

For those whose patient records are audited as part of the study, variables a)-d) and f)-h) will be reported.

# 7 Analysis

#### 7.1 Outcomes

### 7.1.1 Primary outcome

Primary feasibility outcomes are:

- Number of PCNs and practices that are recruited to participate in the study.
- Proportion of target number of audits completed, overall and within each practice based on its stratified sampling target.

• Proportion of participants with dementia for whom service use data is extracted from medical records at participating practices.

The primary implementation outcome is a binary measure that records whether or not a recruited person with dementia has a personalised care plan in place by the end of the study. For each participant where an audit of notes is conducted, the binary variables:

- 1. "Does the person living with dementia have a care plan?" (YES/NO)
- 2. "Did the person with dementia and/or their carer attend the meeting" (here a 'meeting' refers to the occasion when a care plan was determined) (YES/NO)

will be used to determine the primary implementation outcome. A person living with dementia with care plan will be classed as having a personalised care plan in place if answers to both 1. and 2. are 'YES'.

### 7.1.2 Secondary outcomes

People living with dementia:

- DEMQOL (Dementia Quality of Life measure)
- EQ5D-5L (quality of life)

Carers of the person living with dementia

- DEMQOL-Proxy (Dementia Quality of Life measure)
- EQ5D-5L Proxy (quality of life)
- NPI (Neuro-Psychiatric Inventory score)

Carers about their health and wellbeing

- HADS (Anxiety and Depressions scale)
- C-DEMQOL
- EQ5D-5L

Service use data from the CSRI (Client Service Receipt Inventory - Adapted for PriDem):

- Number of each of the following service uses/outpatient appointments during follow-up:
  - o Geriatrician
  - Hospital memory clinic
  - Speech and language therapist
  - Neurologist
  - Psychiatrist
  - Physiotherapist
  - Occupational therapist

- Psychologist
- Other hospital outpatient appointment
- Number of each of the following emergency service uses during follow-up:
  - o NHS Direct or 111 Call
  - o Emergency (999) Call
  - Paramedic attendance only
  - o Paramedic attendance AND transport to hospital by ambulance
  - o Accident and Emergency attendance without ambulance transport
- Number of instances of the following overnight/inpatient stays during follow-up:
  - Unplanned (emergency) hospital stay
  - o General medical planned (elective) hospital stay
  - Psychiatric inpatient hospital stay
  - Specialised rehabilitation service overnight stay
  - Local or district rehabilitation overnight stay

#### 7.2 Primary outcome Analysis

For feasibility, continuous outcomes will be summarised using summary statistics at each time point (for example mean, median, standard deviation, maximum and minimum). Categorical variables will be summarised at each time point using counts and percentages.

For implementation, the primary outcome will be summarised as the proportion of people who have a personalised care plan with an associated 95% confidence interval. In addition, a one-sided, one-sample Z-test at the 5% significance level will be used to test the null hypothesis that the proportion of people with a personalised care plan = 0.4 against a one-sided alternative that this proportion is > 0.4.

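### The primary test, its interval and the 90% power treat audited patients as independent, although audits are drawn by practice; if the result is to inform wider primary care, the error rate and power are misstated

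*SAP*

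**What the plan says.** Section 7.2 of the SAP reports the primary implementation outcome as one pooled proportion: "the primary outcome will be summarised as the proportion of people who have a personalised care plan with an associated 95% confidence interval". The interval method is not named. The accompanying test is a one-sample, one-sided Z-test of 0.4 at the 5% level.

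Section 4.2 sizes that test. It says that "a sample size of 215 people with dementia is sufficient to detect an increase in the proportion of people with a personalised care plan", where the rise in question is 0.1 or more and the power 90%. It adds: "This assumes that the current proportion of people who have a personalised care plan is 0.4".

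The data are grouped. There are four PCNs, and "It is anticipated that each recruited PCN will contain up to 5 practices", which gives at most 20 practices. Section 7.1.1 measures audit completion overall and "within each practice based on its stratified sampling target". Section 4.1 says that sites, as well as participants, are exposed to the intervention.

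One of the two primary implementation objectives in section 3.2 is to assess "If the PriDem intervention can be implemented in wider primary care settings".

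No section mentions an ICC, a design effect, a practice or PCN term, or a clustered variance. Sections 7.4 and 7.5 plan no sensitivity or subgroup analyses. Section 7.2.1 says in general terms that assumptions will be checked, but does not name independence or give a remedy.

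**The concern.** The outcome is whether a care plan exists and whether the patient or carer attended the meeting that produced it. That plausibly depends on how each practice organises its care, and the intervention is delivered to sites. Two patients of one practice are then likely to be more alike than two patients of different practices.

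The one-sample Z-test and the 215 both assume that this correlation is zero. If it is positive and practices stand for a wider population, the variance of the pooled proportion is larger than the analysis assumes. A true null would be rejected more often than 5% of the time, an interval without cluster adjustment would be too short, and 215 audits would give less than 90% power. This is the only hypothesis test specified for the primary implementation outcome.

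**Working it through.** **Inputs from the SAP.** Null proportion 0.4, target 0.5, one-sided 5% level, 90% power, n = 215, four PCNs of up to five practices (all section 4.2); one-sample Z-test (section 7.2).

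**Assumptions, not in the SAP.** 215 audits spread equally over 20 practices, the most that section 4.2 allows, so m = 215/20 = 10.75 per practice; practice ICC of 0.01, 0.05 or 0.10.

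**Step 1: reproduce 215.** With independent observations and the variance at the target, n = (1.645 + 1.282)² × 0.5 × 0.5 / 0.1² = 214.1, rounded up to 215. Power at 215 is 90.1%. The figure is correct for independent patients and contains no allowance for clustering.

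**Step 2: design effect.** DE = 1 + (m − 1) × ICC = 1 + 9.75 × ICC, and the effective sample size is 215/DE.

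**Step 3: true one-sided error of the planned test.** 1 − Φ(1.645/√DE). At ICC 0.05: 1 − Φ(1.645/1.220) = 1 − Φ(1.349) = 8.9%.

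**Step 4: coverage of a nominal 95% interval without cluster adjustment.** 2Φ(1.96/√DE) − 1. At ICC 0.05: 2Φ(1.607) − 1 = 89.2%.

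**Step 5: power of a cluster-adjusted test at 215.** Let SE0 = √(0.24 × DE/215) and SE1 = √(0.25 × DE/215).
- Normal quantiles: Φ((0.1 − 1.645 × SE0)/SE1). At ICC 0.05: Φ((0.1 − 1.645 × 0.0407)/0.0416) = 79%.
- t reference on 20 − 1 = 19 df: the probability that a noncentral t with noncentrality 0.1/SE1 exceeds 1.729. At ICC 0.05 the noncentrality is 0.1/0.0416 = 2.40, and the power is 75%.

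**Step 6: half-width of the adjusted 95% interval near 50%.** 2.093 × SE1, against 1.96 × √(0.25/215) = 6.7 points with independence.

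| Quantity (20 practices) | ICC 0.01 | ICC 0.05 | ICC 0.10 |
|---|---|---|---|
| Design effect | 1.10 | 1.49 | 1.98 |
| Effective n | 196 | 145 | 109 |
| True one-sided error | 5.8% | 8.9% | 12.1% |
| Coverage of naive 95% interval | 93.9% | 89.2% | 83.7% |
| Adjusted power, normal quantiles | 88% | 79% | 68% |
| Adjusted power, t on 19 df | 85% | 75% | 64% |
| Adjusted half-width, t on 19 df (points) | 7.5 | 8.7 | 10.0 |

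**Step 7: fewer clusters.** With 12 practices (m = 17.92) and ICC 0.05, DE = 1 + 16.92 × 0.05 = 1.85, the true error is 11.3%, coverage is 85.1% and adjusted power is 71% with normal quantiles. If the correlation lay at PCN level only (four clusters, m = 53.75) with ICC 0.02, DE = 1 + 52.75 × 0.02 = 2.05 and the true error is 12.6%.

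**The case against.** The strongest objection concerns the target of inference. A reader might conclude that the interval is too narrow whatever the purpose. The SAP does not support that. If practices are fixed strata, all sampled in proportion to size, and the question is about their own patients, differences between practices add no sampling variance. With half the practices at 60% and half at 40%, the stratified half-width is 1.96 × √(0.24/215) = 6.5 points, slightly below the naive 6.7. This part stands, so the point has to be conditional. But the SAP nowhere limits inference to these practices, and section 3.2 names wider settings as a primary objective.

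It can be answered that section 3.2 lists the increase in care plans and the wider implementation as separate objectives, and that the test serves the first. That is fair. Nor are the four PCNs described as a random sample, so a clustered interval would not by itself license generalisation. It would only remove one known understatement of uncertainty.

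A second objection is that this is a non-randomised feasibility and implementation study, and section 4.2 itself says that a formal power calculation would not be appropriate. The same section then claims 90% power, and section 7.2 sets a formal 5% test. The context lowers the severity but does not remove the point.

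A reader might also infer that unweighted pooling biases the estimate towards practices that complete their audits. The SAP does not support this as it stands. It makes audit completion a feasibility outcome without saying that shortfalls are expected, and it does not give the allocation rule. If allocation is proportional and the targets are met, the pooled proportion is self-weighting.

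**Conclusion.** The point holds conditionally. The sample size and the test assume independent patients, the SAP describes audits grouped by practice, and nothing in it deals with the grouping. Once the result is carried beyond the participating practices, any positive practice ICC raises the error above 5%, makes an unadjusted interval too narrow and takes the power below 90%.

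Only the direction is certain. The size rests on an ICC that the SAP does not give, equal practice sizes, and the maximum of 20 practices. ICC 0.01 does little harm to the test: 5.8% error, with power falling mainly because of the t reference. ICC 0.10 more than doubles the error and leaves roughly a one-in-three chance of missing a true rise to 50%. Having fewer than 20 practices makes matters worse. Severity: should be fixed, rather than must be fixed, given the study type and the unknown ICC.

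**What to change.** In section 7.2, compute the interval and the test of 0.4 with practice as the cluster, using either a cluster-robust variance or an analysis of practice-level proportions, with a small-sample correction and a t reference. Name the interval method and report the observed ICC. In section 4.2, restate the power of 215 over a range of ICCs and the expected number of practices.

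If inference is meant only for the participating practices, section 7.2 should say so, and the wider-settings conclusion should not rest on this test. In either case, state as a limitation that four PCNs are too few to estimate variance between PCNs. Weighting by practice is needed only if allocation or audit completion departs from proportional.

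The cost is SAP wording, slightly more analysis, a wider interval and a lower stated power. No additional patients are needed if the lower power is accepted. Restoring 90% by the normal-quantile calculation would take about 215 × DE = 236, 320 or 425 audits at ICC 0.01, 0.05 or 0.10. At 10.75 audits per practice this means about 22, 30 or 40 practices, more than section 4.2 foresees.

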#### 7.2.1 Model checking

Assumptions made when conducting hypothesis tests or fitting models will be checked.

## 7.3 Secondary outcome analyses

The secondary outcomes will be assessed using analogous methods to those used for the primary outcome. All analyses of secondary and other outcomes should be considered as supportive analyses.

## 7.4 Sensitivity analyses

There are no planned sensitivity analyses.

## 7.5 Subgroup analyses

There are no planned subgroup analyses.

## 7.6 Missing data

All analyses will be complete case, with no adjustment made for missing data. Numbers of missing observations will be summarised at each time point for each variable.

#### 7.7 Adverse event reporting

The number, causality, expectedness and severity of adverse events (if any) will be reported at each time point. The number of participants who experience adverse events will likewise be reported.

# 8 Summary of Changes

This Statistical Analysis Plan does not propose any changes to the statistical approach described in the protocol.

Any changes to the Statistical Analysis Plan made after this document has been signed off will be recorded. In addition, significant changes will be fully justified and approved before implementation.
